The Eligibility Screening will consist of the following questions:

- 1) Are you between ages 18-99 years old? [YES TO QUALIFY]
- 2) Have you ever used the SinuSonic device? [NO TO QUALIFY]
- 3) Do you meet any of the conditions listed under the Safety and Warnings for use of the SinuSonic device? [NO TO QUALIFY]
 - a) Current or history of breathing problems (i.e., asthma, chronic obstructive pulmonary disorder (COPD), chronic bronchitis, emphysema, pneumonia, pleural effusion, lung cancer, cancer of the throat or upper airway)

- b) Current or history of circulatory problems (i.e., active nose bleed, heart arrhythmia, coronary artery disease, congestive heart failure, heart attack)
- c) Other conditions, specified as brain tumor, moderate to severe ear pain, fever greater than 101 degrees

- 4) Have you experienced symptoms of nasal congestion that have persisted at least 2 weeks? [YES TO QUALIFY]
- 5) Is your current level of nasal congestion at 5 or higher? (VAS included here) [YES TO QUALIFY]

Step 2: Consent/Linkage File

When all eligibility criteria are met, individuals will be invited to access the Informed Consent document (also provided via RedCap) to read and e-sign. Phone number and email address for the researcher will be provided in the event of questions or request for clarification.

After receiving the e-signed informed consent, researchers will assign a SubjectID number so that the participant can use the SubjectID number when completing all questionnaire assessment sessions using RedCap. Researchers will maintain a database linking SubjectID and name on their password-protected computers that will not be accessible to anyone who is not affiliated with the research.

Step 3: Pre-SinuSonic assessment

Participants will be asked to complete this assessment, via RedCap, prior to beginning use of the SinuSonic. Researchers will provide participants with a link to the assessment (text or email), along with their unique SubjectID number to use. The following instruments will be programmed into RedCap for completion:

Prior to SinuSonic Use (week 0):

- 1) Demographic Information Form
- 2) SF12 to assess overall health ("how you feel and how well you are able to do your usual activities")
- 3) TNSS to assess current nasal symptoms
- 4) BPQ to reflect perception of autonomic regulation
- 5) HADS to assess anxiety and depression
- 6) ATES to assess history of trauma/adverse events

Step 4: SinuSonic Use / Weekly assessments

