After completing the pre-SinuSonic assessment, researchers will inform participants to begin directed use of the SinuSonic (2 minutes per day, 2 times per day). Participants will be asked to confirm SinuSonic use on a weekly questionnaire. Additionally, participants will be asked to complete the following questionnaires approximately 5 minutes after final SinuSonic use for that week. The following instruments will be programmed into RedCap for completion:

Weekly, for 4 weeks (end of week 1, 2, 3, 4).

- 1) TNSS to assess current nasal symptoms
- 2) PGIC to reflect change in activity limitations, symptoms, emotions and overall quality of life

Step 5: Final research assessment

Participants will be asked to confirm use of the SinuSonic on a weekly questionnaire. Additionally, participants will be asked to complete the following questionnaires approximately 5 minutes after final SinuSonic use on the 5th consecutive week. The following instruments will be programmed into RedCap for completion:

End of Study (end of week 5).

- 1) TNSS to assess current nasal symptoms
- 2) PGIC to reflect change in activity limitations, symptoms, emotions and overall quality of life
- 3) BPQ to reflect perception of autonomic regulation
- 4) HADS to assess anxiety and depression

Description of Measures

Body Perception Questionnaire (BPQ) (Cabrera et al., 2018). The Body Perception Questionnaire (BPQ) is a self-report measure of body awareness and autonomic reactivity. Its items are based on the organization of the autonomic nervous system (ANS), a set of neural pathways connecting the brain and body. These pathways send information from the body about the status of organs and tissues (i.e., afferent projections). Some of these incoming signals form a basis for the subjective awareness of the body. The ANS also carries signals that control the functions of these organs and tissues (i.e., efferent projections). These signals can alter the functions of the body, depending on internal and external needs. Only the Autonomic Reactivity subscale will be distributed and used for the current study.

Hospital Anxiety and Depression Scale (HADS) (Zigmond & Snaith, 1983). HADS is a fourteen-item scale with seven items each for anxiety and depression subscales. Scoring for each item ranges from zero to three. A subscale score >8 denotes anxiety or depression.

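### The safety exclusions are asked once, at screening, and the described procedure does not re-check the transient ones before participants are told to start

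*Combined protocol and SAP*

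**What the plan says.** All the safety exclusions sit in Step 1 (Recruit/Eligibility Screening), question 3, which purchasers reach through a QR code on a flyer packed with the device: "Do you meet any of the conditions listed under the Safety and Warnings for use of the SinuSonic device? [NO TO QUALIFY". One qualifying answer is given for the whole question. Three lists stand under it:

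- 3a: "Current or history of breathing problems (i.e., asthma, chronic obstructive pulmonary disorder (COPD), chronic bronchitis, emphysema, pneumonia", continuing with three further lung and airway conditions.
- 3b: "Current or history of circulatory problems (i.e., active nose bleed, heart arrhythmia, coronary artery disease, congestive heart failure, heart attack".
- 3c: "Other conditions, specified as brain tumor, moderate to severe ear pain, fever greater than 101 degrees".

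Step 2 follows: "When all eligibility criteria are met, individuals will be invited to access the Informed Consent document". After e-signature, researchers assign a SubjectID. In Step 3 researchers send a link by text or email: "Participants will be asked to complete this assessment, via RedCap, prior to beginning use of the SinuSonic". The week-0 set is a demographic form, SF12, TNSS, BPQ, HADS and ATES. Step 4 gives the trigger for use: "After completing the pre-SinuSonic assessment, researchers will inform participants to begin directed use of the SinuSonic". During use, "Participants will be asked to confirm SinuSonic use on a weekly questionnaire", together with TNSS and PGIC. Week 5 adds BPQ and HADS.

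**The concern.** An exclusion for a passing state is useful only if it describes the participant at the time it is meant to protect. Here it describes the participant at screening, while use starts several steps later on a researcher's instruction. Contact is remote and the device is self-applied, so no visit is described at which a new fever or nose bleed would be noticed. What is at stake is that the study could instruct someone to begin while that person meets one of the study's own exclusions.

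A second, separate matter is the wording. If the time frame of an item is unclear and one answer covers every condition, respondents may read the question differently, and the answer does not show which condition applied.

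**Working it through.** The protocol gives no figure on this point, so the check is a reading of Steps 1 to 5 in order, plus one count.

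**Count of conditions in question 3.** List 3a names 8 (asthma, COPD, chronic bronchitis, emphysema, pneumonia, pleural effusion, lung cancer, throat or upper-airway cancer). List 3b names 5 and list 3c names 3. Total: 8 + 5 + 3 = 16. Three of these are by nature states that come and go within a short time: the nose bleed in 3b, and the ear pain and fever in 3c. Pneumonia also resolves, but 3a covers history as well as current illness, so a past episode still counts on a literal reading.

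**Sequence from the check to first use.**

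| Step | What happens | Safety item repeated? | Time limit stated? |
|---|---|---|---|
| 1 | Online screening, question 3 | Asked here | No |
| 2 | E-consent, then SubjectID assigned by researchers | No | No |
| 3 | Link sent by researchers, six week-0 forms completed | None listed | No |
| 4 | Researchers tell the participant to begin | None listed | No |
| 4 and 5 | Weekly and final questionnaires | None listed | Not applicable |

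**Could a week-0 form do the job indirectly?** As described under Description of Measures, TNSS covers congestion, sneezing, itching and rhinorrhea. BPQ is limited to autonomic reactivity, HADS covers anxiety and depression, SF-12 covers general health domains, and ATES covers past adversity. None is described as asking about fever, ear pain or bleeding. Even if an item touched on one of these, the start instruction in Step 4 depends on the assessment being completed, not on what was answered.

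**Consequence.** A participant who truthfully answers no to question 3, and then develops one of the three states before finishing the week-0 forms, meets every stated condition for the start instruction. This follows from the text and needs no assumption about rates.

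**Wording of the time frames.** The stem of 3b takes in past as well as present problems, while its first item is limited to a nose bleed that is active. Both cannot govern the same item. List 3c gives no time frame, so it is not said whether a fever last month counts. Taken literally, a stem that includes history widens the exclusion. It can turn away someone with a past nose bleed, but it does not admit anyone who has a listed condition now.

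**The case against.** The strongest reply is that other protection probably exists. Question 3 itself refers to the device's warnings, participants are purchasers who have received the device, the consent pages are not visible, the wording of the start message is not given, and researcher contact details are offered at consent. This stands as a limit on the point. A reader might infer that question 3 is the participant's only safeguard; the documents do not support that. They support only that the described procedure contains no re-check. The sponsor has nevertheless made these conditions study criteria, and the start instruction comes from the researchers, so a warning elsewhere does not show that the criteria hold when that instruction is sent.

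Four other strong readings should also be set aside:

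- That the mixed time-frame wording is what lets an ineligible person start. It is not: it over-excludes, and the gap arises from timing alone.
- That someone febrile on the day of screening is shut out for good. The protocol describes no re-screening route, but it does not forbid one, and the purchaser keeps the flyer and its code.
- That the enrolled population cannot be reproduced. The direct conflict affects one listed item, and how 3a to 3c are laid out in RedCap is not stated.
- That a number of affected participants can be given. If 0.5% to 2% of people had one of the three states on the start day (an assumption with no basis in the documents), then 50 × 0.005 = 0.25 to 50 × 0.02 = 1 of 50 would be affected. This illustrates scale only. The screening-to-start interval could be under a day or many days.

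It is also fair to say that this is a 50-person pilot, that none of its analyses changes, and that directed use continues for five weeks after the start. A check at week 0 says nothing about conditions that arise later.

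**Conclusion.** The point holds in limited form. The transient exclusions are asked once, and the start instruction is tied only to completion of the week-0 forms. On the text, a participant who comes to meet an exclusion after screening is told to begin. The expected number is probably small but cannot be estimated from the documents. The conclusion rests on two readings: that the week-0 set is complete as listed, and that completing it is the sole condition for the start message, as Step 4 states.

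The time-frame conflict in 3b and the missing time frame in 3c are a separate and smaller defect: they make the answer ambiguous without making it unsafe. Taken together, this is an inexpensive improvement worth making, not a flaw that undermines the study's estimates.

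**What to change.** 1. Repeat the protocol's own transient question 3 items on the existing week-0 RedCap form, and send the start message only when the existing criteria are still met.
2. Record question 3 by condition, so that the data show which one applied.
3. Have those responsible reconcile the time-frame wording in 3a to 3c with the device warnings, and with Steps 3 and 4, so that each condition has a stated time frame and the protocol says when eligibility is confirmed.

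No clinical rule, maximum interval or re-screening allowance is proposed; those are for the people responsible to decide. The cost is three repeated items and branching in forms that already exist, a short amendment, a slightly longer form and an occasional delayed start. The re-check covers the start of use only, not the five weeks that follow.

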Short-Form Health Survey-12 (Ware et al., 1995). The SF-12 is a health-related quality-of-life questionnaire consisting of twelve questions that measure eight health domains to assess physical and mental health. Physical health-related domains include General Health (GH), Physical Functioning (PF), Role Physical (RP), and Body Pain (BP)

Total Nasal Symptom Score. The Total Nasal Symptom Score (TNSS) is the sum of scores for each of nasal congestion, sneezing, nasal itching, and rhinorrhea at each time point, using a four point scale (0–3), where 0 indicates no symptoms, a score of 1 for mild symptoms that are easily tolerable, 2 for awareness of symptoms which are bothersome but tolerable and 3 is reserved for severe symptoms that are hard to tolerate and interfere with daily activity. TNSS is calculated by adding the score for each of the symptoms to a total out of 12.

Adverse Traumatic Experiences Scale (ATES) (Kolacz et al., 2020). This measure asks about childhood adverse experiences, childhood maltreatment, other person maltreatment, life-threatening situations, sudden deaths of close ones, and personal health situations. Respondent-reported prior adverse events

of maltreatment, life-threatening situations, and sudden deaths of close ones are summed to create an adversity score (range: 0–19).

Patient Global Impression of Change (PGIC) (Hurst & Bolten (2004). The self-report measure Patient Global Impression of Change (PGIC) reflects a patient's belief about the efficacy of treatment. PGIC is a 7 point scale depicting a patient's rating of overall improvement. Patients rate their change as "very much improved," "much improved," "minimally improved," "no change," "minimally worse," "much worse," or "very much worse."

Data Analyses

Questionnaire data will be entered by participants into RedCap for researcher access. Researchers will export the data into SPSS for data analyses. All databases will be stored on password protected computers, accessible only to researchers affiliated with the study, and backed up on UNC servers.

As the current proposal is for a feasibility/pilot study, researchers will evaluate the following aims to determine whether a larger, randomized trial is warranted.

Aim 1: Examine associations between nasal congestion, autonomic functioning, adverse events, and mental health indices (depression, anxiety) at baseline. Pearson correlation analyses will be used to evaluate relationships among measures at each timepoint.

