Aim 2: (*These would be the aims for a future, randomized clinical trial, with preliminary testing using data from the current feasibility/pilot study*): Evaluate the effect of the SinuSonic on users with chronic nasal congestion. We will focus on three constructs important to psychological and physical health and hypothesize that:

- A) Nasal congestion will significantly improve when comparing baseline measures to follow-up measures at each week, and will maintain effects at 5 weeks. Repeated measures ANOVA will be used to evaluate mean change in outcome measures across time in PGIC and TNSS.
- B) Autonomic functioning will significantly improve when comparing baseline measures to end of study. Repeated measures ANOVA will be used to evaluate mean change in BPQ across time.
- C) Mental health indices (depression, anxiety) will significantly improve when comparing baseline measures to end of study. Repeated measures ANOVA will be used to evaluate mean change in HADS across time.

Aim 3: (*This would be an aim for a future, randomized clinical trial, with preliminary testing using data from the current feasibility/pilot study*). Evaluate the mediating effect of current/previous adverse experiences on outcome measures at 5 weeks, using regression models.

Aim 4: Calculate effect sizes for each outcome variable, which will be necessary to determine adequate sample size for a future clinical trial. G-Power software will be used to determine sample sizes based on the effect sizes of the current outcome measures.

References

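### Participants qualify on a congestion VAS that is never repeated, while the congestion hypothesis is tested only on the PGIC and a four-symptom total in which congestion is at most 3 of 12 points

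*Combined protocol and SAP*

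**What the plan says.** All references are to the combined protocol and SAP.

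- **Step 1, Eligibility Screening, question 5.** The respondent is asked "Is your current level of nasal congestion at 5 or higher? (VAS included here", and yes is the qualifying answer. No range or anchors are given for the VAS.
- **Step 3 (week 0), Step 4 ("Weekly, for 4 weeks (end of week 1, 2, 3, 4") and Step 5 ("End of Study (end of week 5").** The nasal instrument on every list is the same: "TNSS to assess current nasal symptoms". The PGIC joins it from week 1. The VAS is on none of these lists, nor in Description of Measures or Data Analyses.
- **Description of Measures.** The TNSS "is the sum of scores for each of nasal congestion, sneezing, nasal itching, and rhinorrhea at each time point, using a four point scale" from 0 to 3, and "TNSS is calculated by adding the score for each of the symptoms to a total out of 12".
- **Data Analyses, Aim 2, hypothesis A.** "Nasal congestion will significantly improve when comparing baseline measures to follow-up measures at each week". The outcomes named for the repeated measures ANOVA are the PGIC and the TNSS. The TNSS congestion item is not named as an outcome.
- **Data Analyses, Aims 1 and 4.** Aim 1 correlates nasal congestion with the other constructs without saying which score represents it. Aim 4 turns the effect size of each outcome into a sample size for the future trial.

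**The concern.** Congestion defines who enters the study and is the subject of hypothesis A, yet neither outcome named for that hypothesis isolates it. The TNSS total adds sneezing, itching and rhinorrhea. The PGIC, as Step 4 describes it, covers activity, symptoms, emotions and quality of life together. The pilot could therefore report a gain in congestion that came from other symptoms, or miss one that was confined to congestion. Aim 4 then passes the resulting effect size to the next trial.

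There is a smaller issue at the gate. A question that shows its own threshold allows a borderline respondent to round up. Unless the number is kept, nobody can later see how many respondents sat at or near 5, or describe how congested the enrolled sample was on the scale that selected it.

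**Working it through.** The plan gives 50 participants with no alpha, power, effect size or SD, so there is no figure of its own to reproduce. The check compares the schedule with the hypothesis, then sizes the dilution.

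**1. Where each measure is taken**

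| Measure | Screening | Week 0 | Weeks 1–4 | Week 5 | Named for hypothesis A |
|---|---|---|---|---|---|
| Congestion VAS | yes | no | no | no | no |
| TNSS total (0–12) | no | yes | yes | yes | yes |
| TNSS congestion item (0–3) | no | yes, within TNSS | yes, within TNSS | yes, within TNSS | not separately |
| PGIC | no | no | yes | yes | yes |

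The VAS is taken on 0 of the 6 occasions from week 0 to week 5. The TNSS congestion item is taken on 6 of 6.

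**2. Weight of congestion in the total.** 3/12 = 25% of the maximum. The other three items supply up to 9 points, so the total can move with congestion unchanged.

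**3. Dilution if only congestion changes.** Assume four items with equal SD s and a common inter-item correlation r; the documents give neither. The variance of the sum is 4s² + 12rs², so its SD is s√(4 + 12r). A shift in one item alone keeps a fraction 1/√(4 + 12r) of that item's standardised effect. Required sample size goes as 1/effect², so it grows by a factor of 4 + 12r.

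| r (assumed) | Fraction kept | Sample-size factor |
|---|---|---|
| 0 | 1/√4 = 0.50 | 4 |
| 0.3 | 1/√7.6 = 0.36 | 7.6 |
| 0.5 | 1/√10 = 0.32 | 10 |

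This is the case of a change confined to congestion. If all four items shifted equally, the total would show 4/√(4 + 12r) of the item's effect: 2.00, 1.45 and 1.26 for the same r. The total can therefore understate or overstate the congestion effect, and the total alone does not show which.

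**4. Why the screening VAS should not be the baseline.** Selecting at 5 or higher makes the next reading fall on average with no device effect, by (1 − ρ) × SD × φ(a)/(1 − Φ(a)), where a = (5 − mean)/SD. Assumed inputs, none of them in the documents: a 0–10 VAS, unselected mean 4 to 6, SD 2 to 2.5, test-retest correlation ρ of 0.5 to 0.8.

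- Smallest (mean 6, SD 2, ρ 0.8): a = −0.5, ratio 0.509; 0.2 × 2 × 0.509 = 0.20 points.
- Middle (mean 5, SD 2, ρ 0.7): a = 0, ratio 0.798; 0.3 × 2 × 0.798 = 0.48 points.
- Largest (mean 4, SD 2.5, ρ 0.5): a = 0.4, ratio 1.069; 0.5 × 2.5 × 1.069 = 1.34 points.

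A separate week 0 reading absorbs fall that occurs before week 0. The interval between screening and week 0 is not stated; if it is very short, part of the fall may remain.

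**The case against.** The strongest reply is that congestion already has a baseline and five follow-ups. The TNSS rates it from 0 to 3 with described severity levels, at week 0 and in each of weeks 1 to 5. This stands. A reader might infer that the VAS is the only congestion-specific rating and that congestion goes unmeasured after screening; the documents contradict that. The VAS is only the one stand-alone congestion scale, and the gap is that the plan does not name the TNSS item as an outcome.

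Three other strong readings also fail.

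- *That only a yes or no is stored.* The note that a VAS is included may mean that respondents complete one in RedCap and that its value is kept. The documents do not say either way.
- *That selecting on one measure and evaluating on another is a defect in itself.* It is not. A value selected at 5 or higher is a poor baseline, and a separate week 0 measure gives some protection against regression to the mean.
- *That a 0–3 item is too coarse beside a VAS.* The planned analysis is of the total, where one step is 1/12 = 8.3% of the range. Step size is also not sensitivity to change, and the VAS range is not given.

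It can fairly be added that deliberate rounding-up at the cut-off is conjecture. Respondents have already bought the device, and the documents point to no motive and give no means of sizing the effect. In a feasibility pilot of 50, a further outcome is partly a matter of preference. These replies limit the severity. They do not answer the mismatch between hypothesis A and the outcomes named for it.

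**Conclusion.** The point holds in a limited form and is a cheap improvement. What rests on the documents alone: the VAS appears only in screening question 5, with its cut-off visible; recording of the number is not stated; it is not repeated; and hypothesis A is tested only on the PGIC and a total of which congestion is at most 25%. It follows that a change in the total need not be a change in congestion.

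The size of the dilution is illustrative. If congestion alone changes, the total keeps about 0.50 to 0.32 of the item's standardised effect, and a trial sized on the total would need about 4 to 10 times the participants of one sized on the item. This rests on equal item SDs and on correlations of 0 to 0.5, and it would not apply if the other symptoms improved as much. The documents do not support saying that congestion lacks a baseline or that the VAS value is discarded.

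**What to change.** 1. At screening, ask for the VAS number, state the scale's range and anchors, store the value, and let RedCap apply the existing cut-off without displaying it.
2. Repeat the same VAS at week 0 and at the end of each of weeks 1 to 5. Specify the week 0 reading, not the screening value, as the baseline. Use the screening value only to describe the sample.
3. Name the 0–3 TNSS congestion item, together with the VAS, as the congestion measures for hypothesis A, Aim 1 and Aim 4. Keep the TNSS total alongside as the broader nasal symptom outcome, and report effect sizes for each.

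The cost is one item per survey, some RedCap branching logic, and one or two more outcomes to report. Naming the TNSS item needs no new question, so that part can be adopted even if the VAS is not repeated.

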Effects of SinuSonic on Psychological and Physical Well-Being

NCT number NCT06268730
Document Date 12/26/2023

Effect of the SinuSonic Device on Psychological and Physical Well-Being in Adults with Nasal/Sinus Congestion
PI (UNC): [name]

Brief background: Chronic nasal congestion impacts the functioning of the ventral vagal complex (VVC), which includes cranial nerves of the face and head (special visceral efferents), along with vagal regulation of the heart and lungs. Physiological compromise of the VVC due to a current or previous adverse experience may allow for worsening nasal congestion, which then has a circular impact back to poorer vagal regulation of the lungs.

This chronic cycle of congestion and poor vagal regulation can likewise impact mental health. Defensive symptoms/behaviors, such as anxiety and depression, are common emergent symptoms of a compromised VVC.

Purpose: The first aim of the study is to evaluate relationships between current/previous adverse events, degree of nasal congestion, perception of autonomic regulation and symptoms of anxiety and depression via self-report questionnaires.

The second aim of the study is to evaluate the effect of the SinuSonic on physical and psychological well-being in individuals with chronic nasal congestion. The SinuSonic is a self-applied nasal device designed to enhance physical well-being by reducing nasal congestion via simultaneous administration of acoustic vibration and gentle oscillating expiratory pressure. The vibration and expiratory pressure stimulate several cranial nerves that are included in the ventral vagal complex (VVC), including the cranial nerves of the face and head (special visceral efferents). According to the Polyvagal Theory (Porges, 1995, 1998, 2001, 2003, 2007), when the VVC is stimulated, the functioning of related cranial nerves and emergent behaviors should improve, supporting a calmer, more regulated nervous system, and improved mental health.

To evaluate the effects of the SinuSonic, self-report questionnaires will be administered (via RedCap) prior to beginning use of the SinuSonic, weekly during directed use of the SinuSonic (2 minutes per day, 2 times per day), and after 5 weeks of use of the SinuSonic. Weekly self-report questionnaires will include amount of SinuSonic usage and degree of nasal congestion. The final, 5-week questionnaires will include degree of nasal congestion, perception of autonomic regulation and symptoms of anxiety and depression.

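### Follow-up outcome surveys are timed from a device session, so a participant who stops or goes a full week without use has no defined assessment, and week-5 results may come mainly from continuing users

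*Combined protocol and SAP*

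**What the plan says.** Step 4 asks participants, in each of weeks 1 to 4, to "complete the following questionnaires approximately 5 minutes after final SinuSonic use for that week". The instruments are TNSS and PGIC, listed under the label "Weekly, for 4 weeks (end of week 1, 2, 3, 4". Step 5 times the final TNSS, PGIC, BPQ and HADS "approximately 5 minutes after final SinuSonic use on the 5th consecutive week", under the label "End of Study (end of week 5". The Purpose section places the final survey "after 5 weeks of use of the SinuSonic".

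There is one weekly item that is not timed from a session. Step 4 states: "Participants will be asked to confirm SinuSonic use on a weekly questionnaire". The Purpose section adds: "Weekly self-report questionnaires will include amount of SinuSonic usage and degree of nasal congestion".

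Under Data Analyses, hypotheses B (BPQ) and C (HADS) are that the measures will "significantly improve when comparing baseline measures to end of study". Hypothesis A compares baseline with each week. All three use repeated measures ANOVA. Aim 4 takes the resulting effect sizes into a sample size calculation for a later randomized trial. No analysis set, missing-data rule or adherence threshold is stated.

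**The concern.** A survey whose due time is a device session has no due time when there is no session. Whether an outcome is collected can then depend on whether the participant is still using the device, and that may be related to whether it is helping.

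The exposure is greatest for BPQ and HADS. Each is measured at baseline and at week 5 only, so an early stopper has no intermediate value to fall back on, and hypotheses B and C depend entirely on the week-5 survey. For TNSS, repeated measures ANOVA in its usual form keeps only participants with complete data, so one week without a survey can remove a participant from the analysis of hypothesis A.

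The study's stated purpose is to supply effect sizes for a larger trial. An effect estimated mainly in people who kept using the device would be carried into that trial's sample size as if it described everyone who starts. Outcomes that were never requested cannot be recovered later by the choice of analysis.

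**Working it through.** **Text check.** The plan gives no figure on this point, so there is nothing to reproduce. Applying the timing rules to four kinds of participant gives:

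| Participant | Result under the written rules |
|---|---|
| Misses some days, uses the device at least once each week | A last session exists every week; all surveys are defined |
| No use in week 3, then resumes | Week-3 TNSS and PGIC have no defined time; the final survey is unclear, because the fifth consecutive week may mean five unbroken weeks of use or the fifth week in sequence |
| Stops for good during week 3 | TNSS and PGIC are defined up to week 3; nothing after that has a session to be timed from, including BPQ and HADS |
| Uses the device throughout | All surveys are defined |

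**Illustrative size.** The documents give N = 50 but no stopping rate, effect size or SD. Everything else below is assumed.

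Let p be the share who stop before week 5, d the mean change in continuing users, and kd the mean change in stoppers.

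- Effect if only continuing users are measured: d
- Effect in all who began use: (1 − p)d + pkd
- Ratio of the two, with SD unchanged: 1 / (1 − p + pk)

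With k = 0 (stoppers do not change), the ratio is 1/(1 − p). A required sample size proportional to 1/d² would be too small by the square of that ratio.

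| p | Lost at week 5, of 50 | Ratio 1/(1 − p) | Squared |
|---|---|---|---|
| 10% | 5 | 1/0.9 = 1.11 | 1.23 |
| 20% | 10 | 1/0.8 = 1.25 | 1.56 |
| 30% | 15 | 1/0.7 = 1.43 | 2.04 |

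With k = 1 the ratio is 1: no bias, only lost data. With k above 1 (for example, people stop because their congestion has cleared) the ratio falls below 1, and continuing users understate the effect.

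**Letting the SD widen.** Mixing stoppers with continuers also increases the spread. For continuing users at d = 0.5 SD and stoppers at 0, the standardised effect in all starters is (1 − p)d / √(1 + p(1 − p)d²). Suppose that effect is used as the between-arm difference of a two-arm trial (two-sided 0.05, 80% power, SD 1). Then n per arm is 2(1.960 + 0.842)²/effect²:

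| p | Effect in all starters | 0.5 / effect | n per arm |
|---|---|---|---|
| 0% (continuing users) | 0.500 | 1.00 | 63 |
| 10% | 0.45/√1.0225 = 0.445 | 1.12 | 80 |
| 20% | 0.40/√1.04 = 0.392 | 1.27 | 103 |
| 30% | 0.35/√1.0525 = 0.341 | 1.47 | 135 |

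**Lost precision alone.** From the noncentral t distribution, the paired effect detectable with 80% power at two-sided 0.05 is 0.404 SD with 50 assessed, 0.427 with 45, 0.454 with 40 and 0.487 with 35. This cost arises even when there is no bias.

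**The case against.** The best defence reads the label and the timing together: the week says when a survey is due, and the five-minute rule only fixes the moment within that week. On that reading the plan does have a calendar, the final survey falls at the end of week 5 for everyone, and the consecutive-week phrase just means the fifth in sequence. There is also a weekly contact about use that needs no session, so low or zero use can be recorded. Timing surveys from a session has merit in itself, because it standardises time since use.

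Much of this stands, and it rules out several stronger readings that a reader might infer:

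- *That there is no calendar at all.* The end-of-week labels are there. What is missing is a day zero, a window, and an instruction for a week without use.
- *That stoppers are not assessed, or that week-5 results describe continuing users only.* Nothing in the documents withdraws a stopper, withholds the survey link or drops the participant from analysis. The documents are silent.
- *That any interruption loses a survey.* Missing some days does not, and someone who stops in week 3 keeps the surveys up to that point.
- *That the effect is necessarily inflated.* Nothing in the documents shows why people stop.

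The defence does not close the gap. The label and the session rule agree for people who use the device and diverge for people who do not, and no text says which then governs. The weekly use item has no BPQ or HADS attached. The Purpose section puts congestion alongside usage in the weekly questionnaires, but Step 4 separates them and times the TNSS from a session.

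**Conclusion.** The point holds as a gap in the assessment schedule. All follow-up outcome instruments are timed from a session, and a participant who stops, or goes a full week without use, has no defined outcome assessment for that week. Week-5 BPQ and HADS, and the Aim 4 effect sizes, may therefore come mainly from continuing users.

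Neither the size nor the direction of any bias can be found from the documents. The range of 11% to 43% overstatement rests on three assumptions: 10% to 30% stop, stoppers change by 0 on average, and the SD is unchanged. The figures per arm rest further on an assumed effect of 0.5 SD and on using a before-after effect as a between-arm one. The change should be made, because it is cheap and determines which data exist.

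**What to change.** 1. In Steps 4 and 5, send every survey at the calendar end of weeks 1 to 5, counted from the date of first directed use, with a stated window (for example ±2 days), to every participant who began use, whatever their use that week.
2. Keep the timing of about 5 minutes after the last session for those who used the device that week. Those who did not use it complete the survey within the same window.
3. In Step 5, replace the consecutive-week wording with the end of week 5 after first use.
4. Record in each survey the date and time of the last session.
5. Under Data Analyses, report Aims 2 and 4 on all who began use, with continuing users as a secondary description, and state how missing surveys are handled.

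The cost is a short wording change, date-based scheduling in RedCap and one added item per survey. Some scores will not be post-session, which the last-session item makes visible, and the reported mean change may be smaller. Session-based timing for continuing users need not be given up.
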